1.2 Clinical Trials of AR101

1.2.1 ARC001 Trial

ARC001 was a multicenter, randomized, double-blind, placebo-controlled study of the efficacy and safety of AR101 in peanut-allergic children and adults 4 to 26 years of age. ARC001 consisted of a screening period, including a screening double-blind placebo-controlled food challenge (DBPCFC), an initial escalation period, an up-dosing period, and a maintenance period, followed by an exit DBPCFC. The primary endpoint of ARC001 was the percentage of desensitization responders, defined as subjects tolerating 300 mg (443 mg cumulative) at the Exit DBPCFC.

A total of 56 subjects were randomized: 29 subjects to AR101 and 27 subjects to placebo. One subject in the placebo group withdrew consent after randomization and before treatment. The intent-to-treat (ITT) population thus comprised 55 subjects: 29 in the AR101 and 26 in the placebo arm. The 2 groups were overall well matched for baseline characteristics including baseline sensitivity in the Screening DBPCFC. Six subjects in the AR101 arm withdrew prior to the Exit DBPCFC.

In the ITT population, AR101 was statistically significantly superior to placebo, with 23 of 29 (79%) desensitization responders in the AR101 group as compared to 5 of 26 (19%) desensitization responders in the placebo group, resulting in a treatment difference of 60% ($P < 0.0001$ by Fisher's exact test). In the completer population (those subjects completing the Exit DBPCFC), 23 of 23 AR101 completers were desensitization responders, resulting in a treatment difference of 81% ($P < 0.0001$ by Fisher's exact test). At the time of the exit visit, the geometric mean for peanut-specific IgE levels were lower for the AR101 group compared with the placebo group; higher for the AR101 group compared with the placebo group for peanut-specific IgG4; and lower for the AR101 group compared with the placebo group for peanut-specific IgE/IgG4 ratio.

AR101 was generally well tolerated. The overall incidence of treatment-emergent adverse events (TEAEs) was 97% for the AR101 treatment group and 85% for the placebo group. One subject (3%) in the AR101 group experienced a treatment-emergent serious adverse event (SAE) of hypersensitivity (verbatim: anaphylaxis) related to treatment. One subject (4%) in the placebo group experienced an SAE of presyncope/hypersensitivity (verbatim: vaso-vagal reaction/anaphylaxis) related to the peanut protein in the Exit DBPCFC, not investigational product (IP). An additional subject experienced a prerandomization, non-treatment-emergent SAE of hypersensitivity (verbatim: slow developing anaphylaxis or biphasic reaction) following the Screening DBPCFC. No placebo-treated subject had an adverse event leading to discontinuation. A total of 4 AR101-treated subjects (14%) experienced an adverse event that led to permanent discontinuation of study treatment. One subject discontinued due to a treatment-related adverse event of eosinophilic esophagitis (EoE), 2 subjects each discontinued treatment due to a treatment-related adverse event of vomiting and 1 subject discontinued due to an adverse event of stomach pain. Two additional AR101-treated subjects withdrew from the study prematurely due to withdrawal of consent or investigator decision. Both subjects also experienced gastrointestinal (GI) adverse events that likely contributed to their withdrawal from the study.

In summary, AR101 appeared to be generally well tolerated, and significantly superior to placebo for reducing clinical reactivity to peanut allergen in peanut-allergic children and adolescents to young adults. AR101 treatment significantly increased the probability of tolerating peanut allergen doses ≥ 300 mg and resulted in favorable changes in clinical markers of peanut allergen immunoreactivity compared with placebo.

1.2.2 ARC002 Trial

All ARC001 placebo subjects who completed the ARC001 study were eligible for rollover into the open-label ARC002 protocol. All subjects on AR101 who passed the ARC001 Exit DBPCFC by tolerating ≥ 443 mg cumulative of peanut protein with no more than mild symptoms were also eligible to enter ARC002.

Group 1 included subjects who completed the placebo arm of ARC001 and consented to enroll in ARC002, crossing over to active treatment using the same dosing regimen used in ARC001, but in open-label fashion. After completion of the Up-dosing Phase, Group 1 subjects underwent a DBPCFC (to a maximum single dose of 600 mg of peanut protein, or 1043 mg of cumulative peanut protein). Subjects who did not tolerate the post-low-dose build-up phase DBPCFC at ≥ 443 mg cumulative were considered escalation failures and were discontinued from the study due to safety concerns. Those subjects who tolerated the DBPCFC at ≥ 443 mg cumulative of peanut protein entered an approximately 3-month (12- to 24-week) Plateau Phase of continued dosing at 300 mg/d.

Group 2 subjects who completed the active AR101 arm of ARC001 and consented to enroll into ARC002 went directly into the 300 mg/d, 3-month Plateau Phase of ARC002. Following completion of the 3-month Plateau Phase, all ARC002 subjects underwent a post-Plateau Phase DBPCFC (to a maximum single dose of 1000 mg of peanut protein, or 2043 mg cumulative).

Based on the total population of 26 Group 1 subjects receiving ≥ 1 dose of AR101, 76.9% of subjects tolerated 300 mg and 65.4% tolerated 600 mg. At the post-Plateau DBPCFC in 40 subjects in Groups 1 and 2, 100%, 90%, and 60% of the subjects tolerated a cumulative peanut protein dose of 443 mg, 1043 mg, and 2043 mg, respectively. These findings demonstrate the persistence of desensitization during daily maintenance treatment with AR101 at 300 mg/d, further supporting the primary endpoint selection in the Phase 3 trial ARC003. The findings also indicate that treatment with AR101 may achieve a maximum tolerated dose of food allergen substantially higher than the dose used for maintenance itself.

The overall profile of AEs observed in ARC002 is consistent with what was observed in ARC001 and with what has been reported in the literature for academic peanut oral OIT clinical trials. These findings continue to support the ongoing clinical development of AR101, and in particular, the safety and tolerability of low-dose maintenance treatment at 300 mg/d.

1.2.3 ARC003 Trial

ARC003 is an ongoing international, multicenter, randomized, double-blind, placebo-controlled study of the efficacy and safety of AR101 in a characterized desensitization OIT regimen in peanut-allergic individuals. The study consists of a screening phase that includes a Screening

phase (including a DBPCFC), and a double-blind OIT treatment phase that includes an initial escalation period, an up-dosing period, and a maintenance period, followed by an Exit DBPCFC.

All eligible subjects receive escalating doses of either AR101 or placebo, randomized in a 3:1 ratio. A DBPCFC will be performed for those subjects achieving the target dose of 300 mg/d and continuing to receive that dose throughout the maintenance period (approximately 24 weeks). Subjects who do not reach 300 mg/d will be considered escalation failures and non-responders for the primary analysis. Each subject will be unblinded when he/she completes the DBPCFC at the end of the approximately 24-week maintenance period and all major data queries for the subject have been resolved. Those who do not pass the DBPCFC at \geq 443-mg cumulative challenge dose level will be considered endpoint failures and non-responders for the primary analysis. The study is being monitored by an independent Data Safety Monitoring Committee (DSMC) that meets regularly at defined intervals.

1.3 Rationale for the Current Study

The rationale for the ARC007 study is to characterize the safety of AR101 in a broader population of children who are highly likely to have been diagnosed as being peanut allergic based on clinical features alone. To date, Aimmune's Phase 2 and Phase 3 randomized controlled trials have included a screening DBPCFC that is used to select a highly sensitive study population (those reacting at or before 100 mg of peanut protein during that challenge). This, in turn, has allowed recruitment of subjects with any value of skin prick test (SPT) or immunoglobulin E (IgE), since the DBPCFC establishes their baseline sensitivity. However, DBPCFCs are associated with a substantial risk of anaphylaxis both at screening and again at exit, especially in the placebo group. During North American screening for ARC003, 240 doses of epinephrine were administered to 457 subjects who reacted to the DBPCFC, 54 (12%) of whom had at least one severe symptom. Three subjects experienced anaphylaxis to the DBPCFC that met seriousness criteria (Vickery et al, 2017). In addition, mechanistic data suggest that the pre-randomization exposure to peanut required by the DBPCFC procedure may induce peanut-specific T cell activation and potentiate allergic inflammation detectable after the DBPCFC (Rust et al, 2017). This residual inflammation related to the screening food challenge may have unintended consequences affecting the safety and tolerability of the initial stages of the desensitization procedure.

Moreover, in the anticipated post-marketing clinical use of AR101, subjects would not be selected for treatment on the basis of a DBPCFC, which is a research tool that is not used in routine clinical practice. The diagnosis and management of peanut allergy in daily practice relies upon a clinical history (by which the clinician establishes the pre-test probability of the diagnosis), and then measuring allergen sensitization with SPT and/or IgE to arrive at a post-test probability of peanut allergy (Roberts and Lack, 2005; Sicherer and Wood, 2013). These assessments are therefore dependent on the predictive power of such tests to confirm the clinical history, and nomograms incorporating the likelihood ratio have been established based on observational studies. In clinical practice, if the post-test probability of peanut allergy remains uncertain because the combination of the test result and the clinical history are indeterminate, then a food challenge may be necessary as an additional procedure to definitively establish known allergy. However, eliciting a convincing history of a recent allergic reaction to peanut establishes a pre-test probability of $> 90\%$, such that a positive test result of any kind effectively

clinches the diagnosis. This obviates the need for a risky food challenge procedure for confirmation, and is the way most food-allergic subjects are diagnosed in practice (Gupta et al, 2013). In addition, supportive clinical decision points (eg, a peanut IgE of ≥ 14 kU_A/L) for diagnosis have been derived from allergen-specific IgE cutoff levels that are 95% predictive (Sampson, 2001), and these decision points have been widely adopted clinically. The objective of the current study is to expand the AR101 safety experience by testing it in a placebo-controlled fashion in this clinical population, which may be more representative of the kinds of subjects likely to be offered therapy, as compared to those reacting at or before 100 mg of peanut protein in a screening DBPCFC conducted during a rigorously controlled pivotal trial.

1.4 Known and Potential Risks and Benefits of AR101

1.4.1 Risks

Peanut is a commonly-consumed food and as such has a well-understood safety profile. Except for allergic reactions in subjects with peanut allergy, it does not cause discernible side effects in humans.

In subjects with peanut allergy, many OIT studies have been performed using procedures and dosing similar to those proposed in this study. In general, the safety profile has been very good across the studies, and based on those studies, approximately 80%, 15%, and < 1% of the subjects are expected to have mild, moderate, or severe symptoms, respectively, during some point in their dosing with peanut OIT. It is important to note that essentially all AEs have been allergy related, predictable, and reversible. The major atypical AE from OIT that has been reported in the literature is EoE, affecting an estimated 3% of OIT recipients (Lucendo et al, 2014), which is thought to be reversible upon dosing cessation.

The up-dosing and daily maintenance doses of peanut OIT may cause allergic symptoms including sneezing, rhinorrhea, urticaria, angioedema, flushing, flares of eczema, ocular, nasal, oral and/or throat pruritus, nausea, vomiting, abdominal discomfort, cough, wheezing, and/or shortness of breath in addition to severe anaphylaxis. The likelihood of a subject experiencing a severe allergic symptom is expected to be lessened by initiating dosing at extremely small amounts of AR101 and by up-dosing under observation in a clinical setting until the maintenance dose is achieved.

There may be a risk that during participation in the trial subjects may decrease their vigilance against accidental peanut ingestion because they believe they are protected from it. This phenomenon has been reported in previous trials; subjects in the trial and their participating families will be warned that they should continue to practice their usual vigilance against accidental ingestion of peanuts or peanut-containing foods.

1.4.2 Benefits

There is no guarantee that participation in this study will help the subject. Information from this study may help researchers to better understand peanut allergy or to develop future tests or treatments to help patients with this condition.

Please refer to the current edition of the AR101 Investigator Brochure for further information regarding the safety profile, risks, and benefits of AR101.

2. OBJECTIVES

2.1 Primary Objective

The primary objective is to assess the safety and tolerability of AR101 when used in a characterized oral desensitization immunotherapy (CODIT)TM regimen for approximately 6 months in peanut-allergic children.

2.2 Secondary Objectives

The secondary objectives are to characterize the frequency of all treatment-related AEs by study period, especially those of interest (defined in Section 7.3.4), and AR101's effect on asthma control and immune parameters.

3. STUDY DESIGN

This is a multicenter, randomized, double-blind, placebo-controlled safety study of AR101 using the CODIT regimen in peanut-allergic children. Up to 500 peanut-allergic children ages 4 to 17 years will be randomized in a 2:1 ratio to AR101, a pharmaceutical-grade peanut allergen formulation, or placebo. The study will consist of a screening phase and a double-blind treatment phase that includes an initial 2-day escalation period and an up-dosing period. Subjects will be approached at the time of enrollment about donating saliva and additional blood samples to support exploratory biomarker analyses in a sub-study ([Appendix 7](#)). Participation in this sub-study is voluntary and requires signing separate consent and assent documents.

After completion of the up-dosing period, all study exit procedures, and treatment unblinding, subjects who received AR101 may participate in an open-label maintenance trial, known as Study ARC011; subjects who received placebo will be offered up-dosing and maintenance treatments with AR101 in Study ARC008. For subjects participating in follow-on studies, both follow-on protocols must be activated at the study site before subjects can complete all of the required ARC007 study exit procedures. Certain procedures (specifically, completion of questionnaires) and treatment unblinding will be completed at a later unscheduled visit if necessary to accommodate institutional review board (IRB) review of the follow-on protocols and shipment of open-label AR101. Additionally, all major data queries must be resolved before subjects complete exit procedures and proceed to a follow-on study. Subjects will remain on blinded study treatment and have an unscheduled visit every 4 weeks or sooner until all exit requirements are met.

The primary endpoint of the study is the frequency of TEAEs, including SAEs, during the overall study period. Secondary endpoints are frequency of premature discontinuation of dosing due to AEs; frequency of premature discontinuation of dosing due to chronic / recurrent GI AEs; proportion of chronic / recurrent GI AEs resolving at 2, 4, and \geq 12 weeks following cessation of dosing; frequency of allergic reaction (hypersensitivity) AEs occurring during up-dosing, normalized for duration of treatment; frequency of anaphylaxis as defined in the protocol; frequency of use of epinephrine as a rescue medication; frequency of accidental ingestions of peanut and other allergenic foods and severity of any resultant reactions; and assessment of asthma control using the Asthma Control Test (ACT) questionnaire and frequency of use of asthma rescue medication (short acting beta-agonists) in subjects with asthma.

Exploratory endpoints include changes in peanut- and peanut component-specific serum IgE and IgG₄ levels, changes in peanut SPT wheal diameter, changes in Total Nasal Symptom Score in subjects with allergic rhinitis, and changes in scores of the food allergy related quality of life questionnaire (FAQLQ) and food allergy independent measure (FAIM) questionnaire.

The Screening/Baseline Period is up to 21 days. Eligible subjects will be randomized in a 2:1 ratio to receive escalating doses of either AR101 or placebo, in 2 phases. Randomization will be stratified by age group (4 to 11 years and 12 to 17 years). Following a 2-day initial escalation phase, the up-dosing phase will be a minimum of 20 to a maximum of 40 weeks in duration in order to achieve the 300 mg/d dose level. Subjects reaching this dose of 300 mg/d will continue for an additional 2 weeks to ensure tolerability of the 300 mg/d dose. If the subject is unable to tolerate the 300 mg dose for the 2-week period, dosing may continue up to a maximum of 48 weeks after Day 1 to ensure tolerability prior to exiting the study. For subjects terminating early for GI AEs, additional observational follow-up will occur monthly in clinic or by phone for up to 6 months or until the symptoms have resolved or stabilized, or the Investigator deems them to be irreversible, according to details described further in Section 6.5.

Beginning at signed informed consent and assent as age-appropriate, all AEs will be evaluated from the onset of the event until the time the event is resolved or medically stable, or until 30 days after the Exit or Early Discontinuation Visit, whichever comes first, with the exception of GI AEs, detailed further below. Adverse events ongoing at the time that study treatment is discontinued may not be determined to be medically stable until 30 days after the Exit or Early Discontinuation Visit has been conducted, in which case additional visits after the Exit or Early Discontinuation Visit may be required. Subjects who discontinue dosing prematurely due to chronic/recurrent GI AEs will complete the Pediatric Eosinophilic Esophagitis Symptom Score (PEESS™ version 2.0) questionnaire and return to the clinic for evaluation monthly for at least 6 months (if the subject is asymptomatic, telephone follow-up with an Investigator may substitute for in-clinic visit, at the Investigator's discretion). If chronic/recurrent GI AEs persist beyond 6 months, subjects are to continue to be followed with monthly clinic visits (telephone follow-up with an Investigator may substitute for in-clinic visit, at the Investigator's discretion) until the symptoms have resolved or are assessed to have stabilized with optimal medical management or the Investigator deems them to be irreversible. The protocol provides additional specific guidance about symptomatic medical management and referrals to a gastroenterologist, as necessary, in Section 7.3.4.2. Treatment will be administered in a double-blind fashion.

A DSMC has been established to monitor the study for safety.

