1. BACKGROUND AND RATIONALE

1.1 Background

Peanut allergy is a common and serious condition that disproportionately affects children and is associated with severe reactions, including life-threatening anaphylaxis. The prevalence of peanut allergy, like other food allergies, has been rising, and is now at high levels, affecting up to 2% of the population (Sicherer and Sampson 2014). The current standard of care in management of peanut allergy is a peanut-avoidant diet, along with education of the patient and family in the acute management of an allergic reaction, including ready access to self-injectable epinephrine. The burden of avoidance and the constant fear of accidental exposure negatively affect the health-related quality of life for patients and their families (Primeau et al, 2000; Avery et al, 2003; Sicherer et al, 2010; Anagnostou et al, 2014).

In addition, peanut-avoidant diets are complicated by the difficulty of interpreting food labels and the presence of undeclared or hidden allergens in commercially-prepared foods (Joshi et al, 2002; Altschul et al, 2001; Vierk et al, 2002). Accidental exposures are common, with 55 percent of food-allergic patients having at least 1 allergic reaction in a 5-year period (Sicherer et al, 1998).

In early clinical trials, oral immunotherapy (OIT) for peanut allergy has demonstrated encouraging safety and efficacy results in creating a change in clinical reactivity that would protect recipients from these accidental exposures (Jones et al, 2009; Hofmann et al, 2009; Blumchen et al, 2010; Yu et al, 2012; Varshney et al, 2011; Anagnostou, et al 2014). All of these studies involved a period of up-dosing with increasing amounts of peanut protein, a period of maintenance therapy, and then an oral food challenge to assess desensitization. Dosing symptoms observed in these studies included rash, wheezing, rhinorrhea, sneezing, itching, abdominal pain, nausea, vomiting, and diarrhea. Most symptoms were mild, consistent with a transient, low-grade allergic reaction, and tended to diminish in frequency with increasing duration of treatment.

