6.3.3 Up-Dosing (Also Referred to as Build-up) Visits

Up-dosing will last from a minimum of 20 weeks to a maximum of 40 weeks and comprise 10 scheduled up-dosing visits (including the first 300 mg dose of the IP), with the potential for unscheduled visits for assessment of dose tolerability, dose reduction, dose re-escalation, or management of AEs. Subjects reaching this dose will continue in the study for an additional 2 weeks to ensure tolerability of the 300 mg/d dose. If the subject is unable to tolerate the 300 mg dose for the 2-week period, dosing may continue up to a maximum of 48 weeks after Day 1 to ensure tolerability prior to exiting the study.

Subjects will return to the clinic every 2 weeks for up-dosing to a maximum daily dose of 300 mg. The first dose of IP at each new dose level will be administered in the CRC under direct observation and medical supervision.

Subjects must be free from active wheezing, a flare of atopic disease (eg, atopic dermatitis), or suspected inter-current illness prior to any dose escalation. Subjects should be maintained on their current, or a reduced, dose level of IP until their flare of asthma, atopic disease, or inter-current illness has resolved.

Subjects should withhold their daily home dose of IP on in-clinic dosing days, but should take all other prescribed medications as scheduled.

Some or all of the following assessments/procedures will be completed during up-dosing visits in the CRC, according to the SOE:

- Return unused capsules to the clinic
- Monitoring for compliance
- Concomitant medication review
- Limited physical examination
- Diet (food allergen exposure) history update
- Pre-dose vital sign measurement (BP, PR, body temperature)
- PEFR (3 attempts are to be performed). Airflow assessment should as far as possible be measured at the same time at each visit.
- IP administration under observation in the clinic
- Post-dose vital sign measurements (BP, PR) within 15 to 30 minutes post-dose, prior to discharge, and at the Investigator's discretion during the post-dose observation period.
- Optional saliva collection at Week 6 Up-dosing Visit ([Appendix 7](#))
- Monitoring for AEs, including allergic symptoms (Section [7.2](#))
- Completion of the Total Nasal Symptom Score Sheet in subjects with allergic rhinitis ([Appendix 8](#))
- Subjects will be reminded to continue to follow a peanut-avoidant diet for the duration of the study.
- Take home capsules for daily dosing until next visit

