## 7 DEFINITIONS, DERIVATIONS, AND CONVENTIONS

### 7.1 Definitions and Derivations

- Study day is calculated as (assessment date – first dose date + 1) for assessments and visits performed on or after the first dose date, and (assessment date – first dose date) for assessments and visits prior to the first dose date.
- Baseline is defined as the last nonmissing value prior to the first dose of randomized study treatment in ARC007.
- Change from baseline is calculated as the observed value after the first dose – baseline value.
- The screening period is defined as the time beginning with the date and time of informed consent through the day prior to randomization.
- Initial escalation is defined as the time beginning with the date and time of the first dose of randomized study product at the study site and ending with the date of the last dose of randomized study product taken prior to up-dosing.
- Up-dosing is defined as the time beginning with the date and time of the first dose of study product at 3 mg at home, and ending with the date and time of first dose at

300 mg at the study site. Up-dosing will be approximately 20 weeks in duration, but may be extended to a maximum of 40 weeks to accommodate dose reductions and re-escalations, if necessary.

- A 300 mg QD period will be defined as the time beginning with the date and time of the first dose of study product at 300 mg at home and ending with the date of the last dose of study product. This period will be ideally approximately 2 weeks in duration at the end of ARC007, but dosing may continue up to a maximum of 48 weeks after day 1 to ensure tolerability of 300 mg prior to exiting ARC007. Some subjects continued to receive 300 mg doses in ARC007 after the expected rollover date while waiting for activation of ARC008 or ARC011 at the study site. The 300 mg doses as a result of the rollover delay will be included in the 300 mg QD period.

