### **9.8.1 Adverse Events**

All adverse events recorded on the adverse event case report form, symptoms recorded on the allergic adverse events case report form, and symptoms recorded on the in-clinic dosing case report will be summarized together.

If symptoms are recorded as part of an anaphylaxis reaction as reported on the Allergic AE or in-clinic dosing form, only the single anaphylaxis reaction event will be summarized and not the individual symptoms.

All reported adverse events will be classified into SOC and preferred term using MedDRA version 19.1.

Treatment-emergent adverse events are defined as those adverse events with onset after the first dose of study product. Adverse events with onset prior to first dose of study product will be included in subject listings, but not summarized. Treatment-emergent adverse events and non-treatment-emergent adverse events will be listed separately. Treatment-emergent adverse events will be summarized for the safety population by age group (4-11 years, 12-17 years, 4-17 years), treatment group (AR101, placebo), and by study period as follows:

- Initial escalation: All events beginning after the first dose of study product on day 1 and prior to the first administration of study product at home. To avoid gaps between study periods, the first administration of study product at home is assumed to be the day after at-home study product was dispensed at Initial Escalation Day 2.
- Up-dosing: All events beginning after the first administration of study product at home during up-dosing and prior to the first dose of 300 mg at home. To avoid gaps between study periods, the first administration of 300 mg at-home dose is assumed to be the day after the clinic visit where 300 mg dose was first tolerated and at-home 300 mg study product was dispensed.
- 300 mg QD: All events beginning after the first dose of 300 mg at home and prior to exit from the study.
- Overall: Across initial escalation, up-dosing, and 300 mg QD periods (first dose to last dose).

Summaries displayed by SOC and preferred terms will be ordered by descending incidence of SOC and preferred term within each SOC. Summaries displayed by preferred term only will be ordered by descending incidence of preferred term. Summaries of the following types will be presented:

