## 10 PRE-DATABASE LOCK BLINDED DATA REVIEWS

Major data queries that have or may have bearing on the safety aspects of the study will be resolved prior to unblinding individual subjects. These include:

- Fulfillment of inclusion/exclusion criteria
- Accidental peanut exposures that resulted in serious adverse events or adverse events
- Severity and relationship to investigational product of serious adverse events and adverse events

The purpose of the predatabase lock blinded data review is for identification of major and minor protocol deviations.

Only ARC007 project team members who are blinded to study treatment assignments (ie, medical monitor, statistician, data manager, sponsor clinical project staff) will be involved in the data reviews.

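### The 300 mg QD adverse-event column mixes a planned period of about 2 weeks with open-ended rollover waiting, so its percentages depend on administrative delay; report the two parts separately.

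*Protocol*

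**What the plan says.** Protocol section 3 sets the hold: "Subjects will remain on blinded study treatment and have an unscheduled visit every 4 weeks or sooner until all exit requirements are met". There are two main conditions. For children going on to a follow-on study, "both follow-on protocols must be activated at the study site before subjects can complete all of the required ARC007 study exit procedures". In addition, "all major data queries must be resolved before subjects complete exit procedures and proceed to a follow-on study". SAP section 10 lists the queries to be closed before a child is unblinded, and one item is "Severity and relationship to investigational product of serious adverse events and adverse events".

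No upper limit on the wait is stated. The protocol synopsis gives 22 to 48 weeks of dosing but exempts children who are waiting, and Protocol 6.4 provides for final visits more than 6 weeks after the scheduled exit. SAP 7.1 reports in the past tense that such waiting occurred.

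SAP 7.1 describes the 300 mg QD period as ideally about 2 weeks, ends it at the last dose, and adds: "The 300 mg doses as a result of the rollover delay will be included in the 300 mg QD period". SAP 9.8.1 assigns adverse events to that period as "All events beginning after the first dose of 300 mg at home and prior to exit from the study". Overall is the union of the three periods, first dose to last dose. SAP 7.2 bases incidence percentages on the number of subjects at risk.

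**The concern.** Characterising treatment-related adverse events by study period is a secondary objective (Protocol 2.2, SAP 3.2). A reader will take the 300 mg QD column as the experience of the first two weeks or so at the target dose. In fact its length for each child is partly set by site activation, supply of open-label product and query resolution, and only children who reached and tolerated 300 mg can contribute the extra time.

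Most tables in SAP 9.8.1 (by system organ class and preferred term, by severity, serious events, events with epinephrine) are subject incidences, and these can only rise as the window lengthens. If the arms reach 300 mg at different times, they may also be followed for different lengths in this column.

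**Working it through.** **The plan's own figure.** Protocol 6.3.3 says that up-dosing will "comprise 10 scheduled up-dosing visits (including the first 300 mg dose of the IP"). Ten steps × 2 weeks = 20 weeks, plus 2 weeks at 300 mg = 22 weeks. This matches the lower end of the stated dosing duration, so T = 2 weeks (300 mg QD) and T = 22 weeks (Overall, fastest child) are the planned window lengths.

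**Assumptions.** The documents give no distribution of the wait w, so I use 0 to 26 weeks. The event probabilities p are illustrative.

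**Crude incidence under constant hazard:** 1 − (1 − p)^((T + w)/T), with p the incidence over the planned T weeks.

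| Wait w (weeks) | 0 | 4 | 8 | 12 | 26 |
|---|---|---|---|---|---|
| 300 mg QD window (weeks) | 2 | 6 | 10 | 14 | 28 |
| Incidence, p = 10% in 2 weeks | 10.0% | 27.1% | 41.0% | 52.2% | 77.1% |
| Incidence, p = 5% in 2 weeks | 5.0% | 14.3% | 22.6% | 30.2% | 51.2% |
| Overall window (weeks) | 22 | 26 | 30 | 34 | 48 |
| Incidence, p = 10% in 22 weeks | 10.0% | 11.7% | 13.4% | 15.0% | 20.5% |

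For example, 1 − 0.9^(10/2) = 41.0% and 1 − 0.9^(30/22) = 13.4%. These two rows describe different events. The common measure is window length: an 8-week wait multiplies the 300 mg QD window by 10/2 = 5 and the Overall window by 30/22 = 1.36. The more frequent event (10% per two weeks throughout) would go from 1 − 0.9^11 = 68.6% to 1 − 0.9^15 = 79.4% in Overall.

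**If the hazard falls.** Protocol 1.1 says that symptoms in earlier studies "tended to diminish in frequency with increasing duration of treatment". Let the hazard during the wait be f times the earlier one. At w = 8 the 10% two-week event becomes 1 − 0.9^((2 + 8f)/2): 27.1% for f = 0.5 and 19.0% for f = 0.25. The Overall example becomes 11.7% and 10.9%.

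**Exposure-adjusted rate relative to no wait:** (T + f·w)/(T + w), with f relative to the rate in the first T weeks. At w = 8:

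| f | 1 | 0.75 | 0.5 | 0.25 |
|---|---|---|---|---|
| 300 mg QD | 1.00 | 0.80 | 0.60 | 0.40 |
| Overall | 1.00 | 0.93 | 0.87 | 0.80 |

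The rate is therefore free of the wait only if the hazard is constant.

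**Arms.** Suppose that two children start together at one site, reach 300 mg at weeks 20 and 24, and are both released at week 34. Their 300 mg QD windows are 14 and 10 weeks. With identical risk (10% per two weeks) that column shows 52.2% v 41.0%, a gap of 11.2 points from observation time alone. Their Overall windows are 20 + 14 = 34 and 24 + 10 = 34 weeks, which are equal. Cutting Overall at the scheduled exit would instead give 22 v 26 weeks: 1 − 0.9^11 = 68.6% v 1 − 0.9^13 = 74.6%, a gap of 6.0 points.

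**The case against.** The strongest defence is that counting all blinded on-drug time is reasonable in a descriptive safety study with no hypothesis tests, and that held children are still in the overall study period that defines the primary endpoint. That stands, and it is why the primary window should not be shortened. Truncation would remove on-treatment events and, as the example shows, could create an imbalance that full follow-up avoids.

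Much is also handled already. The initial-escalation and up-dosing columns contain no waiting time, the allergic-reaction endpoint is confined to up-dosing and normalised for duration, several tables carry exposure-adjusted rates, and SAP 9.5 shows exposure by period and in 28-day bands. Planned duration varies for clinical reasons anyway. All of this stands, but none of it separates planned from waiting time inside the 300 mg QD column.

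A reader might infer that the hold biases the primary endpoint between arms. The documents do not support this. Activation of both follow-on protocols is required whatever the arm, and under blind. The two conceivable mechanisms, earlier arrival at 300 mg on placebo and more adverse-event queries on AR101, pull in opposite directions, and no passage gives waiting times by arm. Nor can one combine the constant-hazard percentages with the falling-hazard rates as if both held: a falling hazard softens the former, and a constant hazard removes the latter.

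**Conclusion.** The point holds for the 300 mg QD column. Its crude incidence depends on administrative waiting time with no assumption about arms. For an 8-week wait, a 10% two-week event reads as about 41% under constant hazard, or 19% to 27% if the hazard during the wait is a quarter to a half of the earlier one. Exposure-adjusted rates in that column move only if the hazard changes. Different observation lengths by arm are possible there, with size and direction unknown.

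For Overall the effect is modest (10.0% to 13.4% in the example; incidence can rise at most 1.36-fold at constant or falling hazard), and no between-arm bias in the primary endpoint is shown. SAP 7.1 names only the wait for follow-on activation; the query wait enters because the period ends at the last dose. Waiting times, event probabilities and f are assumptions. This is a cheap improvement to by-period reporting, not a flaw in the primary analysis.

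**What to change.** Keep the Overall window, first dose to last dose, for the primary endpoint. In SAP 7.1, 9.5 and 9.8.1, split 300 mg QD into:

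- (a) the planned period, to the scheduled Exit Visit (14 days after the 300 mg visit at which home dosing continued, later only where 300 mg was not yet tolerated);
- (b) the administrative extension, from then to the last dose.

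Give each part its own number at risk, subject-years, subject incidence and exposure-adjusted rate. With this split, the 10% two-week event stays at 10.0% in (a) for every value of w.

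State which visit the word exit denotes. SAP 9.5 ends Overall exposure at the last dose before the exit visit, SAP 9.8.1 counts 300 mg events until exit from the study, and Protocol 6.4 treats exit as complete only at the final unscheduled visit. Events and subject-time should share one cut-off.

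An Overall table truncated at scheduled exit may be added as a sensitivity analysis only. The cost is SAP wording, one derived date per subject and a larger table set. No study procedure changes and no event is dropped.
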